### 1.2.1 Overview of Pasireotide (SOM230)

Pasireotide (SOM230) is a cyclohexapeptide SSA with the following chemical name: (2Aminoethyl)carbamic acid (2R,5S,8S,11S,14R,17S,19aS)-11-(4-aminobutyl)-5-benzyl-8-(4-benzyloxybenzyl)-14-(1H-indol-3ylmethyl)-4,7,10,13,16,19-hexaoxo-17-phenyloctadecahydro-3a,6,9,12,15,18-hexaazacyclopentacyclooctadecan-2-yl ester, di[(S)-2aminosuccinic acid] salt. Like natural somatostatin and other SSAs, pasireotide exerts its pharmacological activity via binding to somatostatin receptors (sst). Somatostatin is an endogenous peptide that modulates a number of exocrine and endocrine secretions. There are five known somatostatin receptors: sst1, 2, 3, 4 and 5. When compared to octreotide, pasireotide has a binding affinity, which is 30-40 times greater for sst1 and sst5, 5 times greater for sst3, and a comparable affinity for sst2 (21,22). Somatostatin receptors are expressed in different tissues under normal physiological conditions as well as in many solid tumors, especially in neuroendocrine tumors where hormones are excessively secreted, e.g. acromegaly, gastroenteropancreatic neuroendocrine tumor (GEP/NET) and Cushing's disease (22-26). A detailed summary of available preclinical data is provided in the Investigator's Brochure (attached).

#### 1.2.1.1 Clinical Experience

##### 1.2.1.1.1 Pasireotide LAR

Pasireotide LAR has been extensively investigated in the clinical development program for healthy volunteers and various patient populations. Completed studies and studies with completed interim analyses are shown in the INVESTIGATOR'S BROCHURE, V15, P. 44, Table 5-1.

Pasireotide LAR demonstrated favorable PK profile for extended release in healthy volunteers and patients. PK steady state was achieved following 3 monthly (q28d) intra-muscular (i.m.) injections of pasireotide LAR in a study with both acromegaly and carcinoid patients. PK exposures of trough concentrations were approximately dose-proportional. CL/F of the Pasireotide LAR formulation was comparable to CL/F of the s.c. formulation (4.3-9.0 L/h). T1/2 for the Pasireotide LAR formulation was approximately 16 days, suitable for monthly dosing. The relative bioavailability of the Pasireotide LAR formulation to the s.c. formulation was complete, ranging from 106% to 148%. PK exposures in acromegaly patients were comparable to those in healthy volunteers. PK exposures in carcinoid patients were 2-fold higher than in healthy volunteers.

The efficacy of pasireotide LAR in acromegaly patients is based on CSOM230C2305, the phase III study to assess the safety and efficacy of pasireotide LAR vs octreotide LAR in patients with active acromegaly. In this study, pasireotide LAR was shown to be significantly superior to octreotide LAR for the treatment of acromegaly in medically naïve patients in terms of biochemical control (GH < 2.5 µg/L and normalization of IGF-1 levels) (31.3% vs. 19.2%; p-value 0.007), providing higher response rate in both de novo patients and in patients with prior pituitary surgery (25.7% vs. 17.3% in de novo patients; 39.4% vs. 21.8% in postsurgical patients). Pasireotide LAR was as effective as octreotide LAR in reducing tumor volume, improving acromegaly symptoms and ring size, and quality of life (27).

Safety and efficacy in humans is summarized in the Investigator's Brochure, version 15, section 5.2. Pasireotide LAR safety is based on studies in patients with Acromegaly, Investigator's Brochure, V15, section 5.2.1.1.3. Safety assessment was based on 491 acromegaly patients who received pasireotide (419 patients received pasireotide LAR and 72 received pasireotide s.c.) in Phase I, II and III studies. The safety profile of pasireotide LAR is consistent with the somatostatin analogs class, except for the higher degree and frequency of hyperglycemia seen with pasireotide LAR. In Study SOM230C2305, the mean duration of exposure to pasireotide LAR across core and extension phase was 75 weeks (N=178).

The most frequent ADRs reported for more than 15% in the pasireotide LAR or octreotide LAR arms core and extension phase were diarrhea (33.1% and 40.6%), cholelithiasis (30.9% and 36.7%), hyperglycemia (28.1% and 7.2%) and diabetes mellitus (19.7% and 3.9%), alopecia (15.7% and 14.4%) and abdominal pain (12.9% and 17.8). Common Toxicity Criteria (CTC) grade 3 or 4 ADRs reported for more than 2% of the patients in the pasireotide LAR and octreotide LAR arms were diabetes mellitus (4.5% and 0%), diarrhea (0.6% and 2.8%) and hyperglycemia (2.2% and 0.6%). ADRs reported in patients who crossed over to the other treatment arm in the Phase III study were similar to those reported in the core and extension.

In the Phase III Study SOM230C2402, The mean duration of exposure in the core phase of Study C2402 was 24 weeks for all treatment groups.

The most frequent ADRs observed for more than 10% in pasireotide LAR 40 mg, 60 mg or active control in the 24-week core phase of study SOM230C2402 were hyperglycemia (33.3%, 29.0% and 6.1%), diabetes mellitus (19.0%, 25.8% and 4.5%) and diarrhea (11.1%, 19.4 and 1.5%), and cholelithiasis (9.5%, 11.3% and 12.1%). CTC grade 3 or 4 ADRs reported for more than 2% of the patients in pasireotide LAR 40 mg, 60 mg and active control were hyperglycemia (11.1%, 8.1% and 0%), and diabetes mellitus (0%, 3.2% and 0%). Adverse drug reactions for Phase III study SOM230C2305 core and extension phase in medically naïve and Phase III study SOM230C2402 in inadequately controlled acromegaly patients with frequency of at least 5% in any pasireotide LAR treatment arm of either study and other notable ADRs which occurred in the two Phase III studies with a frequency of equal or less than 5% are: anemia, adrenal insufficiency, hyperglycemia, diabetes mellitus, type II diabetes mellitus, impaired glucose tolerance, dizziness, headache, diarrhea, sinus bradycardia, QT prolongation, abdominal pain, abdominal distention, nausea, cholelithiasis, alopecia, injection site reaction, increased blood creatine phosphokinase, increased blood glucose, increased alanine aminotransferase, increased glycosylated hemoglobin, and increased blood amylase (27).

## 2 RATIONALE

### 2.1 Study Rationale and Purpose

There is currently no option for medical therapy of CNFA, in general, or specifically of silent corticotroph tumors. Silent corticotroph tumors can range from being completely asymptomatic to becoming large and causing significant hypothalamic/pituitary dysfunction and visual symptoms, and most data support that this type of tumor has a more aggressive phenotype (10,18,19). Current therapy consists primarily of surgical removal of the tumor and for recurrent or residual tumors, repeated surgery and/or radiotherapy. In very aggressive tumors, chemotherapy has been tried with some success (20). Therefore, a need exists for a medical therapeutic option for the treatment of this tumor type.

Corticotroph cell tumors rarely respond to the somatostatin analogs octreotide or lanreotide. However, some data suggest that the multi-receptor somatostatin analog Pasireotide, which is effective for Cushing's disease, may be effective for some silent corticotroph tumors. Analyses of the somatostatin receptor profile of silent corticotroph tumors suggests that the receptor profile of silent corticotroph tumor cells would confer a more favorable response of this tumor type to pasireotide. In two studies, silent corticotroph tumors were found to have 200-fold higher SSTR1mRNA than nonfunctioning tumors, 17-fold higher than Cushing's disease tumors and 5-fold higher SSTR2mRNA than CD, but lower SSTR5 mRNA than CD (28). Given Pasireotide has demonstrated high binding affinity for SST1, 2, 3 and 5, there is good rationale to investigate the utility of pasireotide therapy of silent corticotroph pituitary tumors.

Our study will take a unique approach to evaluate the efficacy of this therapy. Our Neuroendocrine Unit laboratory, under the direction of [name], has developed an assay for plasma POMC. Utilizing measurement of POMC with this assay, we will investigate the efficacy of pasireotide in lowering POMC levels and determine if POMC measurements can serve as a marker for efficacy of pasireotide therapy for silent corticotroph adenomas. Since change in pituitary tumor size is currently the only marker available for monitoring efficacy of treatment of silent corticotroph tumors, the findings of this study could be an important addition to the treatment of patients with silent corticotroph adenomas.

In our ongoing "Prospective Study of Clinically Nonfunctioning Pituitary tumors" funded by the NIH (DK073040), we are prospectively studying a large cohort (currently 285) of patients who have presented with apparent clinically nonfunctioning pituitary tumors. One AIM of this study has been to identify silent corticotroph pituitary tumors based on measurement of plasma POMC levels. All patients have been screened with POMC measurements and POMC levels have been followed over time in patients who had elevated levels, in many also after surgical removal of the pituitary tumor. A number of patients in this cohort have been identified with levels of POMC above our normal range. Those patients with elevated plasma POMC levels were found to have pituitary tumors positive for ACTH on immunohistochemical analysis. We have also examined another group of patients with known silent corticotroph pituitary tumors and some of these patients have been found to have elevated plasma POMC levels. We hypothesize based on the rationale described above that these patients with clinically silent corticotroph pituitary tumors (ACTH positive on pathology) and elevated POMC levels in plasma will respond to pasireotide therapy. Detection of a lowering of the increased plasma levels of POMC by pasireotide would show that POMC measurement is a clinically relevant marker to follow during pasireotide treatment of silent corticotroph tumors. POMC levels could also

serve as a marker that identifies patients in whom pasireotide would be more likely to be effective. Although we do not have evidence yet that pasireotide will produce shrinkage of silent corticotroph tumors, POMC lowering may be associated with tumor shrinkage since somatostatin analog therapy typically produces tumor shrinkage when the biomarker of the tumor is suppressed reflecting tumor cell suppression. This will be tested in this study by examining tumor size changes along that of POMC levels in patients with silent corticotroph tumors.

Thus, our preliminary results suggest that plasma POMC levels will be a useful marker for silent corticotroph pituitary tumors. In this project, we will examine the use of plasma POMC level as a marker for the effectiveness of medical treatment of silent corticotroph tumors with Pasireotide.

[figure not shown]

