## PROTOCOL SUMMARY

**Protocol number:** CSOM230GUS44T

**Title** PILOT STUDY OF PASIREOTIDE LAR TREATMENT OF SILENT CORTICOTROPH PITUITARY TUMORS AND EFFECTS ON PLASMA LEVELS OF POMC

**Clinical Phase:** Phase II

**Investigation Type:** Drug

**Study Type:** Interventional

**Purpose and Rationale:** The purpose of this trial is to test the main hypotheses that Pasireotide LAR treatment of patients with silent corticotroph pituitary tumors and elevated or normal plasma POMC levels will reduce plasma POMC levels and this will be associated with a reduction in pituitary tumor size.

**Primary Objective:** To determine the efficacy of Pasireotide LAR to suppress plasma levels of POMC in patients with silent corticotroph pituitary tumors.

**Secondary Objectives:** To determine the effect of Pasireotide LAR therapy on pituitary tumor volume in patients with silent corticotroph pituitary tumors.

**Study design:** This is an open-label, 12-month pilot study of Pasireotide LAR therapy of 10 patients with silent corticotroph pituitary tumors. Pasireotide LAR 40 mg will be administered monthly. Baseline and monthly visits on therapy will monitor plasma levels of POMC, other pituitary function, safety labs, glucose tolerance, physical examination, and visual fields. Pituitary MRI will be done at baseline, 6 months and 12 months of therapy. The starting dose is Pasireotide LAR 40 mg/month given as intramuscular injection. The dose will be increased to 60 mg/month at 6 months if a fall in POMC levels and/or tumor shrinkage are not attained. LAR will be administered monthly with the last injection at Week 44.

**Study Population:** The eligible patient population will consist of adult patients with known silent corticotroph pituitary tumors and elevated or normal plasma levels of POMC.

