
There is currently no option for medical therapy of CNFA, in general, or specifically of silent corticotroph tumors. Silent corticotroph tumors can range from being completely asymptomatic to becoming large and causing significant hypothalamic/pituitary dysfunction and visual symptoms, and most data support that this type of tumor has a more aggressive phenotype (10,18,19). Current therapy consists primarily of surgical removal of the tumor and for recurrent or residual tumors, repeated surgery and/or radiotherapy. In very aggressive tumors, chemotherapy has been tried with some success (20). Therefore, a need exists for a medical therapeutic option for the treatment of this tumor type. This project assesses this clinical need.

This protocol is a pilot study of the efficacy of Pasireotide LAR for the treatment of silent corticotroph pituitary tumors that have elevated plasma levels of POMC. We hypothesize that elevated plasma POMC levels will be a marker for this tumor type and the response of this tumor type to Pasireotide LAR therapy.

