### 3 INVESTIGATIONAL PLAN

#### 3.1. Overall study design

This is an open-label, 12-month pilot study of Pasireotide LAR therapy of 10 patients with silent corticotroph pituitary tumors.

Pasireotide LAR 40 mg will be administered monthly. Baseline and monthly visits on therapy will monitor plasma levels of POMC, other pituitary function, safety labs, glucose tolerance, physical examination, and visual fields. Pituitary MRI will be done at baseline, 6 months and 12 months of therapy.

The starting dose is Pasireotide LAR 40 mg/month IM, this will be increased to 60 mg/month at 6 months if a fall in POMC levels and/or tumor shrinkage are not attained. LAR will be administered monthly with the last injection at Week 44.

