## 4 Statistical methods

### 4.1. Efficacy assessments

Specific Study Endpoints:

1. Percentage of patients with suppression of POMC level.
2. Percent change from Baseline of POMC level at each visit.
3. Percent change from Baseline of POMC level at final visit.
4. Percent change from baseline in pituitary tumor volume.
5. Change from baseline of fasting insulin or glucose levels or insulin sensitivity indices.
6. Change in HbA1C level

The primary outcome will be differences in POMC from baseline to 12 months after Pasireotide LAR therapy. We will also assess differences in POMC/ACTH ratios from pre to post-treatment. Changes in pituitary tumor size from pre to post-pasireotide therapy will be assessed. Patient characteristics will be summarized by descriptive statistics. Frequencies and percentages for categorical variables and mean, standard deviation, median, minimum and maximum for continuous variables. The paired t-test and Wilcoxon signed test will be used to evaluate the change in POMC level from baseline to final study visit as appropriate. Peptide levels and ratios will be compared by nonparametric approach. Repeated measures ANOVA will also be used to analyze the change in POMC levels over time during pasireotide therapy. Statistical Analysis will be performed by SAS 9.3.

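### Does Section 4.1 need a named analysis linking the fall in POMC to tumor shrinkage?

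*Combined protocol and SAP*

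**What the plan says.** The Protocol Summary hypothesizes that treatment will lower POMC and that "this will be associated with a reduction in pituitary tumor size". Section 1.1 expects that elevated POMC "will be a marker for this tumor type and the response of this tumor type to Pasireotide LAR therapy". Section 2.1 sets out to "determine if POMC measurements can serve as a marker for efficacy of pasireotide therapy for silent corticotroph adenomas" and states that "lowering of the increased plasma levels of POMC by pasireotide would show that POMC measurement is a clinically relevant marker to follow". The same paragraph is more cautious about the tumor: "Although we do not have evidence yet that pasireotide will produce shrinkage of silent corticotroph tumors, POMC lowering may be associated with tumor shrinkage". It then says how the link will be approached: "This will be tested in this study by examining tumor size changes along that of POMC levels".

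The objectives table in Section 2.2 has two rows: POMC change to 12 months (primary) and tumor volume change to 12 months (secondary/exploratory). Section 4.1 gives a paired t-test or Wilcoxon test and a repeated measures ANOVA for POMC, and a nonparametric comparison for peptide levels and ratios. For the tumor it says "Changes in pituitary tumor size from pre to post-pasireotide therapy will be assessed". Section 4.2 powers the POMC change only.

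**The concern.** A main hypothesis and an aim to judge POMC as a marker of efficacy seem to have no analysis behind them. That two quantities are *associated* can mean that both fall on treatment, which the two change endpoints cover. It can also mean that patients with a larger POMC fall have more shrinkage, which nothing in Section 4.1 covers. A claim that POMC marks response needs the second meaning, because both means can fall while POMC says nothing about whose tumor shrank.

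If the method is left open, the choice of coefficient, baseline value and time point, and the handling of withdrawn or dose-raised patients, could be settled after the data are seen. The sentence saying a POMC fall would by itself show a relevant marker adds to the worry, since a fall alone shows only a pharmacodynamic effect.

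The dose rule in Section 3.1 is a further complication: "this will be increased to 60 mg/month at 6 months if a fall in POMC levels and/or tumor shrinkage are not attained". It acts on both variables, so it could distort their relation at 12 months.

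**Working it through.** **1. The plan's own power figure.** Inputs from Section 4.2: mean fall 20%, SD 15%, n = 10, two-sided 0.05. Noncentrality = (20/15) × √10 = 4.22 with 9 df. Power by noncentral t is 96.2%, which agrees with the stated >90%. With 8 evaluable patients (assumed) it is 89.6%. None of this depends on the association question.

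**2. Promise set against plan.** The marker language sits in the summary's purpose statement, the background and the rationale. The objectives table has no association row, and each row it does have is matched by an endpoint in Section 4.1. The visit schedule puts POMC and MRI together at V1, V8 and V14, so the pairs exist without new data.

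**3. What a coefficient would deliver at n = 10.** The approximate 95% interval for Spearman r is tanh(atanh r ± 1.96 × SE), with SE = √[(1 + r²/2)/(n − 3)].

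- r = 0.6: atanh = 0.693, SE = √(1.18/7) = 0.411, interval -0.11 to 0.90.
- r = 0.8: atanh = 1.099, SE = √(1.32/7) = 0.434, interval 0.24 to 0.96.
- n = 8 (assumed): -0.25 to 0.93 and 0.09 to 0.97.

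Simulated power of a two-sided 0.05 Spearman test (critical |r| 0.648 at n = 10, 0.738 at n = 8), for assumed true correlations of 0.6 and 0.8, is about 39% and 76% at n = 10, and 28% and 59% at n = 8. The documents give no correlation, so these are illustrations.

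**4. Does the dose rule make a pre-stated analysis essential?** Carry the Section 4.2 inputs back to 6 months (an assumption). The chance of no POMC fall is p = Φ(−20/15) = 0.091. Let q be the chance of no shrinkage, assumed 0.3 to 0.5.

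- Independent measures, rule read as *either not attained*: 10(p + q − pq) = 3.6 to 5.5 patients.
- Independent measures, rule read as *both not attained*: 10pq = 0.3 to 0.5 patients.
- Correlation 0.6, volume change SD 20% with mean -10% or 0 (all assumed): 3.3 to 5.1 patients (*either*) and 0.7 to 0.8 (*both*).

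In a simulation of 400,000 patients with that correlation, the 6-month Spearman value is 0.58. Suppose patients meeting the rule gain a further 10- or 20-point fall in both measures. The 12-month value is then 0.23 to 0.37 under *either* and 0.50 to 0.55 under *both*.

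That calculation keeps every patient. The discontinuation text in Section 3.3.2 withdraws patients whose tumor enlarges. In the simulation 93% to 98% of those meeting the *either* rule have a volume change at or above zero. If any enlargement means withdrawal, only 0.1 to 0.2 of 10 patients are dose-raised. Among those retained, the coefficient drops by about 0.03 to 0.05: from 0.44 to 0.39–0.40 (mean -10%), and from 0.38 to about 0.35 (mean 0). Most of the loss from 0.58 is then range restriction caused by withdrawal. If growth of up to 10% or 25% is tolerated (assumed), the 12-month value is about 0.2 to 0.34. The result turns on an undefined term and on assumed inputs.

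**5. What a change-on-change correlation can address.** Sections 1.1 and 2.1 also propose that the POMC level itself identifies patients likely to respond. That concerns baseline level as a predictor. Correlating the two changes would not test it.

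**The case for a change.** The best argument for a change is that the Protocol Summary calls the association a main hypothesis and Section 2.1 promises a test. Looking at the changes side by side names no measure, time point or rule for withdrawn patients. A small sample gives a late choice of method more influence. The cost would be one descriptive analysis on data already scheduled, and the primary test would not move.

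Much of this is right. Section 4.1 is silent, and the two mean changes cannot show that POMC tracks shrinkage within patients. A per-patient plot with one coefficient and its interval, without a significance threshold, would be a sensible thing for the analyst to produce. What does not follow is that the plan is defective without it. The aim is exploratory, no listed objective goes unanalysed, and the plan already says the two changes will be viewed together. The coefficient can also be near zero when every patient responds alike, so it would have to be read with the mean changes in any case. The sentence that overstates what a POMC fall would show is rationale prose, hedged within its own paragraph, and no decision rule depends on it.

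**Conclusion.** No change to the plan is needed. The missing link analysis is a gap in detail for an exploratory aim of a 10-patient open-label pilot, and analysts would fill it sensibly from the paired visits. The primary POMC test and its 96.2% power are unaffected. At n = 10 an observed correlation of 0.6 would be compatible with anything from about -0.11 to 0.90, so naming the coefficient in advance would not settle the marker question. A large distortion from the dose rule cannot be claimed: it depends on the reading of that rule, on what counts as enlargement, and on an assumed correlation, volume spread and added effect. Any report should keep the marker interpretation modest and should not present a change-on-change correlation as evidence that baseline POMC predicts response.

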## 2.2 Study Objectives

	Objective	Endpoint
Primary	To determine the efficacy of Pasireotide LAR to suppress plasma levels of POMC in patients with silent corticotroph pituitary tumors.	Change in plasma POMC levels from baseline to 12 months of Pasireotide LAR treatment.
Secondary/Exploratory	To determine the effect of Pasireotide LAR therapy on pituitary tumor volume in patients with silent corticotroph pituitary tumors.	Changes in pituitary tumor volume from baseline to 12 months of Pasireotide LAR Treatment.

